8.4.2 Secondary Endpoints

8.4.2.1 The overall event-free survival with a second predefined cut-off

The event free survival will be analyzed in the same manner as the primary endpoint analysis with the exception that the dichotomous MBT result will be based on a second predefined cut-off: Any PDR_{peak} value of less or equal to 7.5 %/h (see **Appendix A** for detailed description of parameter calculation) will be considered as 'high risk' and any value above that threshold will be considered as 'lesser risk'.

Exalenz Bioscience Ltd.	Last update: August 8, 2019
SAP for Protocol CON-EX-0217: Companion protocol for the ¹³C-Methacetin Breath Test using the BreathID® MCS System for Conatus phase 2 study of Emricasan, an Oral Caspase Inhibitor, under protocol IDN-6556-17 (IND111463)	Document Version: 1.0
Document N°: CSD00109	Page 15 of 21

8.4.2.2 *The one-year event-free survival*

The one-year event free survival will be analyzed in the same manner as the primary endpoint analysis with the exception of censoring all subjects after 1 year (365 days) from baseline MBT date.

This analysis will be repeated while using the second pre-defined cut-off described in the first secondary endpoint (section 8.4.2.1).

8.4.2.3 *The event free survival when using all the repetitions of the MBT measurements (time dependent parameter)*

The event free survival will be analyzed in the same manner as the primary endpoint analysis with the exception of using all repetitions of the MBT measurements while dividing the prediction times to the intervals between tests by applying the Time dependent covariate method.

This analysis will be repeated while using the second pre-defined cut-off described in the first secondary endpoint (section 8.4.2.1).

8.4.2.4 *The six-month event-free survival*

The six-month event free survival will be analyzed in the same manner as the primary endpoint analysis with the exception of censoring all subjects after six months (180 days) from baseline MBT date.

This analysis will be repeated while using the second pre-defined cut-off described in the first secondary endpoint (section 8.4.2.1).

8.4.2.5 *The event-free survival considering only new hepatic decompensation events as defined in Conatus study protocol IDN-6556-17*

The event free survival will be analyzed in the same manner as the primary and secondary endpoint analyses (sections 8.4.1, 8.4.2.1, 8.4.2.3 and 8.4.2.4) taking only hepatic decompensation events into consideration as defined and adjudicated in the Conatus study protocol IDN-6556-17:

1. All-cause mortality
2. New decompensation events

Exalenz Bioscience Ltd.	Last update: August 8, 2019
SAP for Protocol CON-EX-0217: Companion protocol for the ¹³C-Methacetin Breath Test using the BreathID® MCS System for Conatus phase 2 study of Emricasan, an Oral Caspase Inhibitor, under protocol IDN-6556-17 (IND111463)	Document Version: 1.0
Document N°: CSD00109	Page 16 of 21

- a. Variceal hemorrhage (including recurrent variceal hemorrhage) documented by endoscopy and requiring hospitalization
- b. New onset ascites requiring diuretics (in a subject without prior history of ascites requiring diuretics)
- c. New onset HE \geq grade II requiring hospitalization in the absence of other comorbidities or alternative causes (in a subject without prior history of HE \geq grade II)
- d. Hepatorenal syndrome requiring hospitalization (either type 1 or 2)
- e. SBP requiring hospitalization

3. MELD score progression defined as any increase \geq 4 points from baseline

This analysis will be repeated while using the second pre-defined cut-off described in the first secondary endpoint (section 8.4.2.1).

8.4.3 *Exploratory Endpoints*

8.4.3.1 *The specific hepatic decompensation type event free survival*

The specific types of hepatic decompensation events or combinations of them for event free survival will be analyzed in a similar manner as the primary endpoint analysis. The following list contains all the separate analyses that will be performed:

1. All-cause mortality
2. Liver-specific mortality
3. Liver-specific mortality **or** liver transplant
4. Liver transplant
5. Variceal hemorrhage that required ‘non-drug therapy’ (e.g. variceal ligation, sclerotherapy) based on the AE log or requiring hospitalization **or** portal hypertensive gastropathy hemorrhage requiring hospitalization
6. Variceal hemorrhage that required ‘non-drug therapy’ (e.g. variceal ligation, sclerotherapy) based on the AE log or requiring hospitalization **or** portal hypertensive gastropathy hemorrhage requiring hospitalization **or** occurrence of

Exalenz Bioscience Ltd.	Last update: August 8, 2019
SAP for Protocol CON-EX-0217: Companion protocol for the ¹³C-Methacetin Breath Test using the BreathID® MCS System for Conatus phase 2 study of Emricasan, an Oral Caspase Inhibitor, under protocol IDN-6556-17 (IND111463)	Document Version: 1.0
Document N°: CSD00109	Page 17 of 21

large varices or varices with red wale signs (classified as severe in the AE log) and that required ‘non-drug therapy’ (e.g. variceal band ligation or sclerotherapy) based on the AE log to avoid hemorrhage

7. New onset ascites requiring diuretics (in a subject without prior history of ascites requiring diuretics)
8. SBP requiring hospitalization
9. New onset ascites requiring diuretics (in a subject without prior history of ascites requiring diuretics) **or** any occurrence of refractory ascites requiring ‘non-drug therapy’ (e.g. paracentesis) based on the AE log (in a subject with history of ascites requiring diuretics) **or** SBP requiring hospitalization
10. New onset HE \geq grade II requiring hospitalization (classified as SAE) in the absence of other co-morbidities or alternative causes (in a subject without prior history of HE \geq grade II)
11. Any onset of HE requiring hospitalization (classified as SAE) in the absence of known co-morbidities or alternative causes
12. Hepatorenal syndrome requiring hospitalization
13. MELD score progression defined as any increase \geq 4 points from baseline
14. All hepatic decompensation events defined in section 8.4.1, except for MELD score progression.

This analysis will be repeated while using the second pre-defined cut-off described in the first secondary endpoint (section 8.4.2.1).

8.4.3.2 *Absolute mean and percent mean change in MBT parameters*

The absolute and percent change in MBT parameters will be summarized descriptively by summarizing the PDR_{Peak} and cPDR_{30min} (see **Appendix A**) changes and percent changes for each treatment group. Due to the small sample expected in this analysis (missing values were not related to outcome), no statistical tests will be applied on that endpoint.

Exalenz Bioscience Ltd.	Last update: August 8, 2019
SAP for Protocol CON-EX-0217: Companion protocol for the ¹³C-Methacetin Breath Test using the BreathID® MCS System for Conatus phase 2 study of Emricasan, an Oral Caspase Inhibitor, under protocol IDN-6556-17 (IND111463)	Document Version: 1.0
Document Nº: CSD00109	Page 18 of 21

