3.3 Rationale to use the MBT for assessment of Liver Disease Severity

Tests of true hepatic function that rely on the metabolism of administered exogenous compounds have not yet been widely adopted in clinical practice because they have been cumbersome to perform and the acquisition of results is slow. The recent development of the BreathID® MCS analyzer offers a unique opportunity to demonstrate a metabolism-based test showing agreement with disease progression and HVPG measures.

In advanced liver disorders, the liver has reduced ¹³C-Methacetin metabolic capacity, leading to low MBT values. Low values of Methacetin metabolism are suggestive of patients who are likely to have advanced liver disease and thus increased portal pressure. Several MBT output variables (percentage dose recovery rate and cumulative percentage dose recovered - PDR/CPDR values at different time points) could be used to assess disease progression.

It has been shown in preliminary studies that MBT correlates with both CTP and MELD values. It may be even more sensitive and a better predictor of liver function because generally function deteriorates prior to the development of complications of cirrhosis and a decline in liver function as assessed by CTP and MELD⁽³⁾.

It is hypothesized that a decline in liver function as assessed by MBT measured serially over time will occur prior to the development of complications of cirrhosis (such as variceal bleeding, ascites and hepatic encephalopathy) and worsening in liver function as assessed by changes in CTP and MELD.

The MBT could therefore produce immediate results to aid in decision making in patients with cirrhosis awaiting liver transplant. Such a test may in future help in decision-making regarding transplantation priority and provide point of care assessment of therapeutic interventions if relevant.

This study's aim is to show the ability of the ¹³C-methacetin breath test to identify patients at risk for decompensation and to determine the effect of Conatus' study drug emricasan on the metabolic capacity of the liver at 24 week intervals of treatment and at final treatment visit at different treatment doses compared to placebo.

Exalenz Bioscience Ltd.	Last update: May 24, 2017
Study Title: Companion protocol for the ¹³ C-Methacetin Breath Test using the BreathID® MCS System for Conatus phase 2 study of Emricasan, an Oral Caspase Inhibitor, under protocol IDN-6556-17 (IND111463)	Protocol: CON-EX-0217 Version: 2.0

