7 ANALYSIS SETS

7.1 *Safety Analysis Set*

The Safety analysis set will include all subjects (randomized and non-randomized into the Conatus emricasan study under protocol IDN-6556-17) that initiated at least one MBT (had taken Methacetin), even if the MBT was not completed or the result was not valid.

7.2 *Intent To Diagnose (ITD) Analysis Set*

The intent to diagnose (ITD) analysis set will include all subjects that were randomized into the Conatus emricasan study under protocol IDN-6556-17 and that had at least one valid MBT result.

7.3 *Per Protocol (PP) Analysis Set*

The per protocol (PP) analysis set will include all subjects from the ITD analysis set who did not have any major protocol deviations and exclude any subject that had a previous transjugular intrahepatic shunt (TIPS) or bariatric surgery that may affect the efficacy of the breath test.

Exalenz Bioscience Ltd.	Last update: August 8, 2019
SAP for Protocol CON-EX-0217: Companion protocol for the ¹³C-Methacetin Breath Test using the BreathID® MCS System for Conatus phase 2 study of Emricasan, an Oral Caspase Inhibitor, under protocol IDN-6556-17 (IND111463)	Document Version: 1.0
Document N°: CSD00109	Page 11 of 21

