7.4 Statistical Analysis of Analysis Sets

The safety analysis set will serve as the principal data analysis set for the safety.

The PP analysis set will serve as the principal analysis set for the efficacy analyses.

The primary and secondary efficacy assessments will also be performed on the ITD analysis set.

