8.4.1 Primary Endpoint

The MBT parameter used to predict hepatic decompensation event is PDR_{peak}. Any PDR_{peak} value of less or equal to 5.5 %/h (see **Appendix A** for detailed description of parameter calculation) will be considered as ‘high risk’ and any value above that threshold will be considered as ‘lesser risk’. The dichotomous MBT result will be tested for significance using the Cox proportional hazards regression model with site and Conatus protocol IDN-6556-17 randomized arm as covariates. If the Conatus protocol IDN-6556-17 randomized arm factor is found non-significant (i.e. p-value > 0.05), then this factor will not be a covariate for the main analysis to be performed. If the Conatus protocol IDN-6556-17 randomized arm factor is found statistically significant (i.e. p-value ≤ 0.05), then the main analysis will be performed keeping this factor as a covariate (to ‘adjust’ the analysis for treatment).

The following list defines the hepatic decompensation events for the primary endpoint:

- Liver-specific mortality
- Liver transplant
- New and/or recurrent hepatic decompensation events

Exalenz Bioscience Ltd.	Last update: August 8, 2019
SAP for Protocol CON-EX-0217: Companion protocol for the ¹³C-Methacetin Breath Test using the BreathID® MCS System for Conatus phase 2 study of Emricasan, an Oral Caspase Inhibitor, under protocol IDN-6556-17 (IND111463)	Document Version: 1.0
Document N°: CSD00109	Page 13 of 21

- Variceal hemorrhage that required ‘non-drug therapy’ (e.g. variceal ligation, sclerotherapy) based on the AE log or requiring hospitalization
- Portal hypertensive gastropathy hemorrhage requiring hospitalization
- Occurrence of large gastroesophageal varices or any varices with red wale sign (classified as severe in the AE log) and that required ‘non-drug therapy’ (e.g. variceal ligation or sclerotherapy) based on the AE log to avoid hemorrhage
- Ascites requiring diuretics (in a subject without prior history of ascites requiring diuretics) or refractory ascites requiring ‘non-drug therapy’ (e.g. paracentesis) based on the AE log (in a subject with history of ascites requiring diuretics).
- Any onset of hepatic encephalopathy (HE) requiring hospitalization (classified as SAE) in the absence of known co-morbidities or alternative causes.
- Hepatorenal syndrome requiring hospitalization
- Spontaneous bacterial peritonitis (SBP) requiring hospitalization
- MELD score progression defined as any increase ≥ 4 points from baseline

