These hepatic decompensation events are identified using the study’s ‘new decompensation event’ dataset as well as events listed in the AE and SAE logs, the reason for (early) termination, the comment and the lab results (incl. MELD scores) datasets. All potential hepatic decompensation events will be adjudicated through a medical review prior to the primary efficacy analysis and blinded to the breath test results. Once defined and adjudicated, the first of the hepatic decompensation events after the first valid MBT will be used for the respective event-free survival analysis.

All MELD scores will be calculated using the formula from the US Organ Procurement and Transplantation Network (OPTN) Policy from 2016 (**Appendix B**). MELD score progression will not include subjects who are started on anticoagulants after the first valid

Exalenz Bioscience Ltd.	Last update: August 8, 2019
SAP for Protocol CON-EX-0217: Companion protocol for the ¹³C-Methacetin Breath Test using the BreathID® MCS System for Conatus phase 2 study of Emricasan, an Oral Caspase Inhibitor, under protocol IDN-6556-17 (IND111463)	Document Version: 1.0
Document N°: CSD00109	Page 14 of 21

MBT (and prior to the identified MELD progression event) that can affect the PT or INR at the time of MELD assessment.

The time-to-first event will be derived as the number of days between the day of the screening MBT test and the date when the first hepatic decompensation event occurs or when a subject is censored (i.e., event/censored date minus screening MBT date plus 1). Subjects will be censored at their last study visit for the following reasons:

- If a subject discontinues the study prior to the end of the study without experiencing a hepatic decompensation event
- If a subject reaches the Final Treatment visit without experiencing a hepatic decompensation event
- If a subject develops hepatocellular carcinoma (HCC)

Survival analysis will be conducted using the Cox proportional hazard model. The model summary will include the number of subjects in the model, and a table with each covariate in a separate line specifying the coefficient's value, Hazard Ratio, Hazard Ratio 95% Confidence Interval and p-value. In addition, a Kaplan-Meier plot for event-free survival will be presented, stratified by MBT parameter along with the MBT parameter log-rank p-value. Additionally a crosstab table of MBT parameter and events will be presented.

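### SAP 8.4.3.1 items 7 and 10 analyse new-onset ascites and encephalopathy without limiting the risk set to subjects who can have the event

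*SAP*

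**What the plan says.** SAP 8.4.3.1 lists 14 separate event-free survival analyses and says that they "will be analyzed in a similar manner as the primary endpoint analysis". Item 7 is "New onset ascites requiring diuretics (in a subject without prior history of ascites requiring diuretics". Item 10 is new-onset HE of at least grade II requiring hospitalization, "in the absence of other co-morbidities or alternative causes (in a subject without prior history of HE" of grade II or higher. Each is repeated at the second PDRpeak cut-off.

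The primary method is in SAP 8.4.1: "The dichotomous MBT result will be tested for significance using the Cox proportional hazards regression model", accompanied by a Kaplan-Meier plot and a crosstab of breath-test class against events. On the population, SAP 7.4 says "The PP analysis set will serve as the principal analysis set for the efficacy analyses". SAP 7.3 has that set "include all subjects from the ITD analysis set who did not have any major protocol deviations", and also drops subjects with previous TIPS or bariatric surgery. Prior ascites and prior HE are not grounds for exclusion. The censoring reasons in 8.4.1 are early discontinuation, hepatocellular carcinoma, and "If a subject reaches the Final Treatment visit without experiencing a hepatic decompensation event". None of them refers to prior history.

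**The concern.** The wording of items 7 and 10 restricts who can have the event. Nothing restricts who is in the denominator. A subject who already had ascites requiring diuretics cannot have event 7, but would contribute event-free time until censoring. The same holds for prior HE of grade II or higher under item 10. The trial enrols decompensated cirrhosis, and the ascites definition in 8.4.1 itself provides for subjects with a history of ascites, so such subjects are to be expected.

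Two outputs are affected. Kaplan-Meier curves and crosstabs would show too much freedom from new onset. The HR would mix the predictive effect of the breath test with any difference between the PDRpeak classes in the share of subjects who are not at risk. The exploratory objective in SAP 3.1.3 is to validate prediction of specific event types, and SAP 8.1 has nominal p-values presented, so a distorted HR could be read as evidence for or against the test.

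**Working it through.** The plan states no prevalence of prior history, event count, HR or power for items 7 and 10, so there is no figure of its own to reproduce. Every prevalence, event rate and HR below is an assumption.

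**1. Does the text retain these subjects?** The wording about prior history appears elsewhere in the SAP:
- The ascites qualifier sits inside the primary composite (8.4.1). The ascites and HE qualifiers both sit inside the composite of 8.4.2.5. In a composite they can only define an event.
- Item 9 joins a limb for subjects without a history of ascites and a limb for subjects with one in a single analysis. Neither limb can be restricting the population there.

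The event-only reading of items 7 and 10 is therefore the more natural one. With the sets in 7.3 and 7.4 and the censoring in 8.4.1, it leaves subjects with prior history in the risk set.

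**2. Kaplan-Meier curves.** If a share p has prior history, and censoring is unrelated to history, apparent cumulative incidence = (1 - p) x incidence among those truly at risk. With p = 70% and a true incidence of 25%: 0.30 x 25% = 7.5%. Freedom from new onset would read 92.5% instead of 75%. This error has the same direction for any p above zero.

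**3. Hazard ratio.** Let pH and pL be the shares with prior history in the high-risk and lesser-risk PDRpeak classes. Early in follow-up, the hazard in each class is the share at risk times the hazard among those at risk, so

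apparent HR ≈ true HR x (1 - pH)/(1 - pL).

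With true HR 2.5, pH 70-85% and pL 50-60%, the extremes are:
- lowest: 2.5 x 0.15/0.50 = 0.75
- highest: 2.5 x 0.30/0.40 = 1.88

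**4. Check by simulation.** Cox models were fitted to simulated cohorts of 20,000 with 40% in the high-risk class, a 20% one-year event risk in lesser-risk subjects who are at risk, and follow-up of 0.92 to 2.0 years.

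| True HR | pH / pL | Formula | Cox, all subjects | Cox, at-risk only |
|---|---|---|---|---|
| 2.0 | 70% / 70% | 2.00 | 1.77 | 1.99 |
| 2.0 | 60% / 50% | 1.60 | 1.41 | 2.00 |
| 2.0 | 80% / 60% | 1.00 | 0.81 | 1.92 |
| 2.0 | 50% / 60% | 2.50 | 2.22 | 1.94 |
| 1.0 | 80% / 60% | 0.50 | 0.51 | 1.07 |
| 1.0 | 70% / 70% | 1.00 | 1.02 | 0.96 |

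For a true HR of 2.0, the full-set fits fall below the formula because the truly at-risk subjects in the high-risk class have their events sooner. Those left in that class are then increasingly subjects who cannot have the event. This explains the mild attenuation even when history is balanced. Restricting the risk set returns approximately the true HR in each row.

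**5. What remains after restriction.** SAP 4.1 expects about 90% of 210 subjects to have a breath test: 0.90 x 210 = 189, before per-protocol exclusions. With an assumed 25% event rate and 40% in the high-risk class, two-sided 5% power for HR 2 by Schoenfeld's formula is:

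| Prior history | Subjects at risk | Events | Power |
|---|---|---|---|
| 50% | 94 | 24 | 38% |
| 70% | 57 | 14 | 25% |
| 80% | 38 | 9 | 18% |

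**The case against.** The strongest reply is that no sentence in the SAP says these subjects are kept. Section 8.4.3.1 asks only for a similar analysis, whereas the secondary endpoints are to be analysed in an identical way. In a single-event analysis the parenthesis could be meant as a population limit. This stands in part: retention is an inference from the rules, not a stated choice. But the use of the same wording in the composites and in item 9 points the other way, and two programmers could produce different results from the present text.

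A reader might also infer that the sickest subjects are the ones counted as event-free, so that the HR is necessarily biased down. The documents do not support that. Protocol 3.3 says that in preliminary studies "MBT correlates with both CTP and MELD values", which makes more prior history in the low-PDRpeak class plausible. It does not establish this for a cohort in which everyone is already decompensated, and no prevalence by class is given. If history were less common in the high-risk class, the HR would be pushed up (2.22 for a true 2.0 in the 50%/60% row).

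Finally, the consequence is limited. Both items are exploratory and outside the testing hierarchy of SAP 6.2. Item 11 counts HE whatever the history, and item 9 includes refractory ascites in subjects with a history. That stands and sets the severity. Those items answer different questions, however, and do not correct items 7 and 10.

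**Conclusion.** The at-risk population for items 7 and 10 is not specified, and the rules as written leave in subjects who cannot have the event. Overstated freedom from new onset follows whenever any subject has the history. The HR is distorted mainly when history differs between PDRpeak classes: about 0.75 to 1.88 for a true HR of 2.5 under the assumed prevalences, with only mild attenuation if history is balanced. Downward bias is the plausible direction but is not demonstrated, and its size rests wholly on prevalences that the documents do not give. Primary and secondary conclusions are unaffected. This is a minor point and a cheap improvement.

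**What to change.** In SAP 8.4.3.1, state that item 7 is analysed only in subjects without prior ascites requiring diuretics, and item 10 only in subjects without prior HE of grade II or higher, each determined at the first valid breath test. Name the data source for that history. Apply the restriction at both cut-offs and to the Cox model, Kaplan-Meier curves and crosstabs, and report the number at risk and the number of events by PDRpeak class. Leave items 9 and 11 on the full set.

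The cost is one sentence and a subset flag that is needed anyway to decide whether an event is new onset. No events are lost, but denominators shrink and perhaps 9 to 24 events remain under the assumed rates. The primary model carries site as a covariate. With the site groups of at least 10 subjects in SAP 8.5, 189 subjects could form up to 18 groups (189/10 = 18.9), so the site-adjusted model may not be estimable in the subset. The SAP should therefore allow descriptive presentation of these two items when events are too few.
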